Do Terpenes Play a Role in the Stress-reducing Effects of a Forest Bathing Intervention?

NCT05316597

May 7, 2024

1. Objectives

Aim 1. Assess whether VOC inhalation regulates stress reduction and affective outcomes of the terpeneson vs. terpenes-off sessions.

Primary physiological outcome: increases in the HF (ms²) component of HRV.

Secondary outcomes: decreases in blood pressure, heart rate, self-reported stress, negative affect, and levels of inflammatory cytokines (IL-6, TNF-alpha, CRP) and cortisol in serum, and increases in positive affect, measured via mobile physiology equipment and blood using standard clinical methods. Hypothesis: VOC inhalation will regulate increases in the HF (ms²) component of HRV and decreases in blood pressure, heart rate, self-reported stress, and levels of inflammatory cytokines in serum as secondary outcomes.

Aim 1a. Assess the degree of association of absorbed dose of seven forest-derived VOCs in serum (i.e., α -pinene, β -pinene, β -myrcene, Δ 3- carene, limonene, β - carophyllene, α -humulene) with these outcomes. Hypothesis: Absorbed dose of seven forest-derived VOCs in serum will be associated with stress reduction and affective outcomes.

2. Design

Potential participants were screened via a phone call and excluded if they were pregnant, smoking, and/or had a current or prior diagnosis of neurologic, hypertensive, psychiatric, respiratory disorder, or anosmia/hyposmia. Participants were also excluded if they were prescribed a short list of prescription medications known to influence terpene metabolic pathways and short-term inflammatory biomarkers including beta-blockers, antibiotics, statins, hypertension medications, steroid medications, and diabetes control medications. Eligible participants were asked to avoid certain foods, beverages, cleaning products, and supplements that contain terpene compounds in the 24 hours leading up to their forest sitting experience.

Additionally, the clinically validated University of Pennsylvania Smell Identification Test (UPSIT) (Sensonics International, Haddon Heights, NJ) was administered to determine whether participants had anosmia/hyposmia. The UPSIT is a 40-item, self-administered "scratch-and-sniff" test that uses microencapsulated odorants that are released by scratching designated spaces on a paper test booklet. Summed scores were used to evaluate olfactory function and identify/exclude participants with undiagnosed smell loss or total anosmia (summed UPSIT score ≤ 18).

Following enrollment, participants were randomly assigned to a sequence of two sessions using a computer-randomized order created by an investigator who was not a member of the field team. To control participants inhalation exposures to terpenes in the forest air, participants wore a powered air-purifying respirators (PAPRs; 3M[™] Versaflo[™] Powered Air Purifying Respirator, TR-800-PSK/94248; 3M, St. Paul, MN). In one session, the PAPR mask was fitted with a particle-only filter (3M[™] Versaflo[™] High-Efficiency Filter, TR-6710N-5) to allow for the inhalation of forest terpenes ("terpenes-on"). In the other session, the mask was fitted with a charcoal filter (3M[™] Versaflo[™] Organic Vapor/HEPA Cartridge, TR-6510N) that removed particles, terpenes, and other BVOCs from the breathing zone ("terpenes-off"). Equipment labels were covered and filters were labeled "A" (later revealed to be "terpenes-off") to blind the study field team and participants to treatment assignment. A washout period of at least eight days between sessions was included to reduce carryover effects (Sibbald & Roberts, 1998).

Forest-sitting sessions took place at the UW Charles L. Pack Experimental Forest located near Eatonville, Washington ("Pack Forest") during June to September 2022 and 2023 to avoid rain, snow, and cold weather. The sessions were 60 minutes each and took place between 10:00 AM and 4:00 PM in a stand of old- and second-growth Douglas Fir, Western Red Cedar, and other conifers accessible by a 10-minute drive on an unpaved single-lane road from the Pack Forest Conference Center. Participants were seated in a comfortable chair, but the session was otherwise unscripted.

3. Methods

We enrolled 43 adult participants between July 12, 2022, and September 21, 2023. Our target sample size of 40 participants was based on the estimated numbers needed to detect minimum differences in the study

outcomes in the contrasting conditions for the same participant, based on the minimums in the ranges of Hedges' g values from prior studies and standard population-level intra-individual differences. Participants were recruited from the Tacoma and Seattle, WA area using physical flyers placed in community centers, libraries, and local universities, and electronic listings on Craigslist and the University of Washington (UW) Institute of Translational Health Sciences study recruitment site. Potential participants were screened via phone call and excluded if they were pregnant, smoking, not fluent in English, and/or had a current or prior diagnosis of neurologic, hypertensive, psychiatric, or respiratory disorder, or anosmia/hyposmia. Participants were also excluded if they were prescribed a short list of prescription medications known to influence terpene metabolic pathways and/or short-term inflammatory biomarkers including beta-blockers, antibiotics, statins, hypertension medications, steroid medications, and diabetes control medications or if they were unable to walk for 15-20 min on unsteady ground. Eligible participants were asked to avoid certain consumer products, foods, beverages, cleaning products, alcohol, marijuana, e-cigarettes, and supplements that contain terpenes in the 24 hours leading up to their forest-sitting experience.

Participants' usual nature contact was assessed using measures from Bratman et al. (2024) and Bratman et al. (2021), based on operationalizations from other nature exposure papers (Shanahan et al., 2016; White et al., 2019). Average nature contact frequency was assessed by presenting asking participants with the following question: "About how often do you usually visit or pass through outdoor natural areas for any reason? This includes, for example, walking, biking, or recreating outside in local, regional, or national parks, at the beach, beside or within lakes, creeks, or the ocean, gardening or tending to plants, camping, fishing, reading or walking outside next to trees, engaging in yard work with natural elements, etc..." Participants selected an answer from following options: "Never", "Once a year", "Once every three months", "Once a month", "2-3 times a month", "Once a week", "2-3 days a week", "4-5 days a week", or "6-7 days a week" (Bratman et al., 2024). Average nature contact duration was measured by presenting participants with the following question: "Over the last month, approximately how many HOURS PER WEEK do you consider yourself to have interacted with nature? This includes, for example, walking, biking, or recreating outside in local, regional, or national parks, at the beach, beside or within lakes, creeks, or the ocean, gardening or tending to plants, camping, fishing, reading or walking outside next to trees, engaging in yard work with natural elements, etc..." (Bratman et al., 2021). Participants entered their response in a provided text box.

Nature relatedness was measured during baseline measurements using the short-form nature relatedness scale (NR-6; Nisbet & Zelenski, 2013). The NR-6 consists of 6 items designed to capture how people view their relationship with nature (e.g., "My relationship to nature is an important part of who I am"). Each item is rated on a 5-point scale, ranging from 1 ("Disagree strongly") to 5 ("Agree strongly") with a total score calculated by averaging all six items. Cronbach's α was used to measure how closely correlated related scale items were as a group. In the current study, NR-6 showed good reliability (Cronbach's α = .76).

HF HRV was measured in milliseconds squared (ms²) using a portable, continuous electrocardiogram sensor (EcgMove4; Movisens®, Karlsruhe, Germany) worn directly on the chest with adhesive electrodes. We applied a natural logarithmic transformation to 5-minute averages of HF HRV ('In-HF HRV') following Shaffer & Ginsberg (2017). Additionally, HF HRV values were winsorized.

Systolic and diastolic blood pressure were measured with an automated cuff monitor (GE Healthcare CARESCAPE V100 Vital Signs Monitor; GE Healthcare, Chicago, IL) in millimeters of mercury (mmHg). HR was also measured with the automated cuff monitor in beats per minute (BPM).

SCLs were measured in microsiemens (μ S) using a portable, continuous electrodermal sensor (EdaMove4; Movisens®, Karlsruhe, Germany) worn on a wristband and attached to the palm with adhesive electrodes.

General levels of positive and negative affect were assessed using the 20-item Positive and Negative Affect Schedule (PANAS; Watson et al., 1988) during baseline measurements and state levels were assessed during the forest-sitting sessions using the 10-item, shortened PANAS (I-PANAS-SF; Thompson, 2007). The PANAS is designed to assess affect over the past month and includes 10 items on positive affect (e.g., "Interested," "Active") and 10 on negative affect ("Distressed," "Irritable"). Each item is rated on a 5-point scale, ranging from 1 ("very slightly or not at all") to 5 ("extremely") with sum positive and negative affect scores calculated. In the current study, the PANAS showed good reliability for positive affect (α = .88) and negative affect (α = .85). On the I-PANAS-SF, 5 items assess positive affect (e.g., "Inspired", "Alert"), and five assess negative affect ("Upset", "Hostile") at the present moment. Each item is rated on a five-point scale, ranging from 1 ("very slightly or not at all") to 5 ("extremely") from which sum positive and negative affect scores were calculated. In the current study, I-PANAS-SF showed good reliability for positive affect (Cronbach's α = .86) and lower reliability for negative affect (Cronbach's α = .40).

Baseline perceived stress was assessed using the four-item version of the Perceived Stress Scale (PSS-4) designed to assess perceptions of stress over the last month (e.g., "In the last month, how often have you felt that you were unable to control the important things in your life?"; Cohen et al., 1983). Each item was rated on a 5-point scale, ranging from 0 ("never") to 4 ("very often") and a sum score was calculated. In the current study, PSS-4 showed good reliability (Cronbach's α = .78). State-level stress during the forest sessions was measured with one item. Participants were asked to rate to what extent they felt stressed at the moment on a 5-point scale, ranging from 1 ("very slightly or not at all") to 5 ("extremely").

Different aspects of the subjective experience of the forest setting were assessed following each session using a combination of questions about the sensory experience and the perceived restorativeness of the forest. Perceived restorativeness was assessed using the adapted 11-item Perceived Restorativeness Scale (PRS-11) which asks participants to rate the degree to which they agreed with statements such as "Places like that are fascinating" using an 11-point scale, ranging from 0 ("not at all") to 10 ("completely"; Pasini et al., 2014), Additionally, participants were asked to rate the pleasantness of their sensory experience of the forest for sight, smell, and visual experience on a 10-point scale ranging from 1 ("not pleasant") to 10 ("extremely pleasant"). Participants were also provided an open-ended text box to describe further thoughts or feelings they had about the sensory experience of the forest.

A trained phlebotomist or registered nurse collected approximately 5 mL of blood via venipuncture before and after each session using BD Vacutainer[™] Push Button Blood Collection Sets into 6 ml BD Vacutainer[™] Venous Blood Collection Tubes (BD, Franklin Lakes, NJ). On the day of collection, samples were stored at room temperature for 30 min to allow clotting, stored at 4°C, then centrifuged at 3,000 rpm for 10 min . Serum aliquots were separated into 2 mL Fisherbrand[™] Externally and Internally Threaded Cryogenic Storage Vials (Thermo Fisher Scientific, Waltham, MA) and stored at -80°C before being transported on dry ice to the Centers for Disease Control and Prevention (CDC) Tobacco and Volatiles Branch (Atlanta, GA) and the UW Center for Studies in Demography and Ecology Biodemography Laboratory (Seattle, WA) for analysis.

Acute cytokine response was assessed using a custom three-plex enzyme immunoassay microarray (Quansys Biosciences, Logan, UT, part number 107749GR) to measure levels of CRP, TNF- α , IL-6, and serum cortisol. Chemiluminescence was quantified using a Quansys Q-view Imager LS. An 8-point, 5-parameter standard curve was used to estimate cytokine concentrations and assay limits of detection (Q-view software, Quansys Biosciences, Logan, UT).

A competitive microplate enzyme immunoassay, previously validated for use with plasma (Munro & Stabenfeldt, 1984), was adapted to measure cortisol in serum extracts using a purified polyclonal anti-cortisol antibody, R4866 (provided by [name], UC Davis), and cortisol reference calibrators (Steraloids, catalog number Q3880). This assay has been used successfully with saliva, urine, hair, and dried blood spot samples (Doyle et al., 2019; Heller et al., 2018; Konishi et al., 2012; Trumble et al., 2010). The anti-cortisol antibody cross-reacts 100% with cortisol, 10% with prednisolone, 6% with prednisole, 6% with 11-deoxycortisol, 5% with cortisone, and less than 1% with all other steroids (data provided by [name]). Color reactions were quantified at 405 nm (test) and 570 nm (reference) using a Synergy HT microplate reader (Bio Tek Instruments, Inc., Winooski, VT). A 5-parameter standard curve was used to estimate cortisol concentrations (Gen5, Bio Tek Instruments Inc., Winooski, VT). For both acute cytokine and cortisol response analyses, all samples, standards, and controls were assayed in duplicate wells.

Concentrations of α -pinene, β -caryophyllene, β -myrcene, β -pinene, Δ -3-carene, and limonene were measured in serum using stable isotope dilution with headspace solid-phase microextraction (SPME) and gas chromatography-tandem mass spectrometry (HS-SPME GC-MS/MS) following Silva et al. (2020). Methods and results are detailed in Riederer et al. (*in preparation*). Briefly, samples were thawed, mixed using a hematology mixer (Fisher Scientific Inc., Pittsburgh, PA), and a 0.50 mL aliquot dispensed into a 10 mL solid phase microextraction vial. Purge-and-trap grade methanol was used to dilute pure chemicals into the primary standard and internal standard (ISTD) stock solutions. A 40 µL spike of the ISTD solution was added the sample, which was then crimp-sealed and mixed with a vortexer (S/P Multi-Tube Vortexer, Baxter Diagnostics Inc., Minster, OH) for 5 min. Vials were placed on a Peltier-cooled sample tray (15°C) on an Agilent 7890 GC (Agilent, Santa Clara, CA) coupled to an Agilent 7010 triplequadrupole MS (Agilent, Santa Clara, CA) with a mounted CombiPAL autosampler and extra PAL autosampler arm (CTC Analytics AG, Zwingen, Switzerland). Samples were analyzed in positive ion electron-impact ionization with multiple reaction monitoring modes. Blank and quality control samples were also prepared with a 40 µL ISTD spike. Standards prepared following an identical method were included with each analytical run. Laboratory blanks consisted of VOC-free water in sealed ampoules opened on the day of analysis. We also collected 7 field blanks on random days comprised of VOC-free water drawn through serum tubes and handled identically to the serum samples.

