## 4. Data Exclusions

## 4.1 Handling Missing Data

We assessed missing data after obtaining a blinded dataset but before being unblinded to the actual treatment per session. Unexpected missing data emerged in the blinded dataset, resulting in the absence of a predefined approach to address this issue prior to data collection. Primary analysis will use a complete case dataset, except for the positive and negative affect outcome. 16 (3.9%) of the 414 questionnaires

were missing 1-2 items at one of the time points, and the impact of missing items will be adjusted for using the number of missing items variable in the model.

We expect the small amount of missingness to have a minimal impact on our results, however we will assess this impact with sensitivity analyses. For comparison, we will perform the analysis on an imputed dataset. We expect this to narrow confidence intervals without greatly impacting the coefficient.

We will be imputing some missing values for two types of data, 1) missing questionnaire items (relevant to secondary outcomes) and 2) missing baseline ln-HF HRV (relevant to primary outcome). The PANAS positive affect (PA) and negative affect (NA) outcomes are scored by summing 5 individual PA and NA items. 16 (3.9%) of the 414 questionnaires were missing 1-2 items at one of the time points, though the data were typically complete for other time points. Because answers for the same item are modestly correlated between timepoints from the same day (mean  $R^2 = 0.58$ ), but still performed better than other imputation approaches (random PA and NA item from the day, mean PA or NA score, and regression imputation), we will use the mean available item value for missing items. This methodology is similar to the mean imputation approach demonstrated in Shrive et al. (2006), but employs individual item row mean imputation, a single item imputation approach that can be used for longitudinal data (Engels and Diehr, 2003).

Brief State Rumination Inventory (BSRI) is a sum of 8 individual items. 6 (4.3%) of the 138 questionnaires were missing 1-2 items. The answers for the same item were correlated with the other time point for the same day (mean  $R^2 = 0.83$ ).

For ln-HF HRV, there were 5 participants whose ln-HF HRV was partially captured both before and during exposure, but missing during the window of our standard baseline time (i.e., B1).

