Additional 5-minute periods of ln-HF HRV were calculated using continuous data from before treatment exposure, including 10-5 minutes before B1 (R1), 5-0 minutes before B1 (R2), 0-5 minutes into the venipuncture procedures (V1), 5-10 minutes into the venipuncture procedure (V2), 0-5 minutes into the drive up to the forest site (D1), and 5-10 minutes into the drive up to the forest site (D2).

Correlations between B1 ln-HF HRV and each additional time point prior to exposure were assessed using a complete case data set.

Time points with the highest correlations (R1, R2, V1, D1) were included in single linear regression models to predict B1 values using a complete case data set. One participant did not have any additional timepoints available, so we used a regression model with the B1 measurement from the other session as a predictor ( $s_{b1}hrv \sim s_{b1}hrv$ ).

Each single linear regression model (b1\_hrv ~ r1\_hrv, b1\_hrv ~ r2\_hrv, b1\_hrv ~ v1\_hrv, b1\_hrv ~ d1\_hrv, s2\_b1\_hrv ~ s1\_b1\_hrv) was cross validated using a complete-case dataset to assess  $R^2$  values (0.92, 0.95, 0.98, 0.85, and 0.83, respectively).

Models were preferentially ranked based on R^2 values and predicted values for B1 will be imputed depending on R1, R2, V1, D1, and S1B1 (session 1 baseline 1) timepoint availability. Of the missing

baseline observations, there is one person for whom we would use V1 to predict B1, three people for whom we would use D1 to predict B1, and one person for whom we would use S1B1 to predict S2B1.

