#### 4.2 Data Exclusion Criteria

Five participants were removed from analysis: two participants who were recommended for exit by IRB staff following responses to study protocols, one participant who withdrew mid-session, and two participants who were found to meet exclusion criteria following their first session.

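### Must the size justification be restated because fewer than 40 complete pairs reach the primary analysis?

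*Protocol*

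**What the plan says.** - **Target and basis.** Protocol Section 3 (Methods): "Our target sample size of 40 participants was based on the estimated numbers needed to detect minimum differences in the study", continuing "outcomes in the contrasting conditions for the same participant". The basis is the smallest Hedges' g values in earlier studies together with typical intra-individual variation. Neither is given as a number.
- **Enrolment.** Protocol Section 3: "We enrolled 43 adult participants between July 12, 2022, and September 21, 2023".
- **Removals.** SAP 4.2: "Five participants were removed from analysis".
- **Primary model.** SAP 3.2 (Primary Analysis) fits a random-intercept model with baseline and filter as covariates, keeps people with only one session, and commits to reporting effect sizes and confidence intervals for the filter effect.
- **Missing data.** SAP 4.1: "Primary analysis will use a complete case dataset, except for the positive and negative affect outcome". Five participants lack ln-HF HRV in the standard baseline window, including "one person for whom we would use S1B1 to predict S2B1". Imputing these baselines is a sensitivity analysis.
- **Indirect session count.** SAP 4.1, on the Brief State Rumination Inventory (BSRI): "6 (4.3%) of the 138 questionnaires were missing 1-2 items", with items "correlated with the other time point for the same day".

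Neither document gives the number of sessions, complete pairs or single-session participants for any outcome.

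**The concern.** The filter effect is estimated mainly within person, so complete pairs drive its precision. A reader sees a target of 40, then 43 enrolled, then 38 analysed, then single-session participants of unstated number, then a complete-case rule that removes more ln-HF HRV sessions. The number that matters most is never printed, and the target cannot be reproduced because its inputs are missing.

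At stake is how a non-significant ln-HF HRV result is read. A reader who took 40 at face value might believe the trial could detect smaller differences than the analysed data allow.

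**Working it through.** **1. The target.** The plan's 40 cannot be reproduced: g, SD or correlation, alpha, sidedness, power and any dropout allowance are all unstated. As an illustration, assume a two-sided 5% test. With 40 complete pairs, the noncentral t gives a detectable difference of 0.454 SD of the paired difference at 80% power, or 0.526 SD at 90%. The 95% CI half-width is t(0.975, 39)/√40 = 0.320 SD.

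**2. People.** 43 − 5 = 38 analysed.

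**3. A ceiling on pairs for the primary outcome.** A participant without a usable baseline in one session cannot form a complete pair. If the five with missing baselines are all among the 38, there are at most 38 − 5 = 33 pairs, even if nobody else missed a session.

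**4. Sessions inferred from the BSRI.** Assume two forms per session day, every form returned, and a count covering only the 38.
- Sessions: 138/2 = 69.
- With each person contributing one or two sessions, pairs = 69 − 38 = 31 and singles = 2 × 38 − 69 = 7.
- The 414 affect questionnaires do not settle the matter. 414/6 = 69 agrees, but the Protocol text describes five affect assessments per session (baseline and T1 to T4), and 414/5 = 82.8 is not whole.

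**5. Complete-case ln-HF HRV, starting from step 4.** 69 − 5 = 64 sessions.
- If all five losses break a pair: 31 − 5 = 26 pairs, 7 + 5 = 12 singles.
- If only the person with a session 1 baseline but no session 2 baseline breaks a pair, and the other four were singles: 30 pairs, 7 + 1 − 4 = 4 singles.

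**6. Precision under the planned model.** Let p be pairs, s singles split evenly between filters, and ρ the within-person residual correlation. Then

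effective pairs = p + s(1 − ρ)/2, and SE relative to 40 pairs = √(40 / effective pairs).

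| Data | Effective pairs (ρ = 0 to 0.75) | SE ratio | CI half-width (SD of difference) |
|---|---|---|---|
| 40 + 0 | 40 | 1.00 | 0.32 |
| 31 + 7 | 34.5 to 31.9 | 1.08 to 1.12 | 0.35 to 0.36 |
| 30 + 4 | 32.0 to 30.5 | 1.12 to 1.15 | 0.36 to 0.37 |
| 26 + 12 | 32.0 to 27.5 | 1.12 to 1.21 | 0.36 to 0.39 |

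For example, 26 + 12(1 − 0.75)/2 = 27.5 and √(40/27.5) = 1.21.

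**7. What this says about power.** It depends on the unstated design power. If 40 pairs had given 80%, 31 + 7 gives 70–74% and the two ln-HF HRV cases give 63–70%. If 40 pairs had given 90%, the figures are 82–85% and 76–82%.

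**8. Does the plan's result depend on any of this?** No. The model uses whatever sessions are available, and its standard error reflects the pairs, the singles and the complete-case losses. Printing the inputs behind 40, or the pair count, changes no estimate, interval or test.

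**The case for a change.** The strongest case for a change is that the Protocol itself frames 40 around a same-participant contrast, so 40 complete pairs is the natural reading. On that reading the analysed data fall short under every count above. The SAP authors already hold the blinded dataset, so a short table of sessions, pairs and singles per outcome would cost almost nothing. A confidence interval alone does not tell a reader how many pairs produced it, or whether the trial met the basis on which it was sized. That the count has to be guessed from a rumination questionnaire, which is neither a listed outcome nor in any planned model, is a fair complaint.

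Part of this stands: the numeric inputs behind 40 and the pair count are missing, and a good trial report would give both. The rest does not carry. The text sets a target number of participants beside an enrolment of 43. If 40 was an enrolment target, it was exceeded. No power is stated that the achieved data can be shown to miss.

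The 31, and the 26 to 30 built on it, are not bounds. Sessions with only one BSRI form returned would mean more than 69 sessions. A count taken before the five removals would mean fewer analysed pairs. BSRI completion also says nothing direct about ln-HF HRV recording, and missing T2 values could lower the primary count further.

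**Conclusion.** No change to the plan is needed. The gap is one of reporting detail, not an arithmetic error: no printed figure is miscalculated, and the stated target is not contradicted unless it is read as 40 complete pairs. On that reading, and on the BSRI inference, the loss of precision is modest: a standard error about 8–12% larger overall and 12–21% larger for complete-case ln-HF HRV, with a CI half-width of at most about 0.39 against 0.32 SD of the paired difference. These sizes assume a within-person correlation of 0 to 0.75, singles split evenly between filters, two BSRI forms per session day all returned, and a count covering only the 38 analysed.

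Recruitment ended in September 2023, so the number of pairs cannot be changed by rewording the justification. A retrospective detectable difference would add little to the observed interval. The SAP discloses the removals, the single-session rule and the missing baselines, and commits to the interval on which a null result should be judged. Counts of pairs and single-session participants belong in the participant flow of the trial report, where analysts would ordinarily give them.
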